4. ESTIMATED DURATION OF THE STUDY

We estimate that the study will take 4 years.

5. LAY LANGUAGE SUMMARY OR SYNOPSIS (no more than one paragraph)

This study will involve treating low back pain associated with nerve injury with two types of medicinal cannabis for eight weeks. Research subjects will consume either oral Δ9-THC (dronabinol), vaporized 4.0% Δ9-THC/6.5% CBD (estimated percentages), or placebo. An analysis will then be performed to assess the risk-benefit ratio of dronabinol and vaporized 4.0% Δ9-THC/6.5%. In addition, subjects will undergo driving simulation to determine how long it takes for them to recover from these medications.

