By conducting repeat assessments for four hours following the first vaporization, we will be able to determine at what point participants no longer exhibit acute effects for each of the study medications. Participants will then complete a second vaporization and ingestion of oral medication before hour 6. We will then assess them for three hours in order to determine whether the acute effects are similar to those seen after the first vaporization, or perhaps greater (due to cumulative/residual effects). To minimize the novelty of the driving simulations, participants will complete a pretest training session to re-familiarize themselves with the hardware and the tasks that they are to encounter during the simulations. Four separate tasks will be embedded within the simulation.

Table 3 Assessments of Acute Effects One Day following 2 and 8 Weeks of Cannabis Treatment

Hour	1		2	3	4	5		6	7	8
		Vaporization/Oral Medication					Vaporization/Oral Medication			
Vital Signs	X		X	X	X	X		X	X	X
Numerical Pain Intensity Score	X		X	X	X	X		X	X	X
Cold Pressor Test	X		X					X		
Pain Relief			X	X	X	X		X	X	X
Psychoactive Effects			X	X	X	X		X	X	X
Driving Simulation	X		X	X		X		X	X	X
iPad Performance Testing	X		X	X		X		X	X	X
Blood Draw ($\Delta 9$ -THC levels)	X		X	X	X	X		X	X	X

Driving simulations: Simulation hardware will consist of a 3-screen, wide field-of-view monitor setup, steering wheel, and accelerator and brake pedals. The fully interactive simulations will assess lane tracking (standard deviation of lateral position [SDLP], or “weaving”), response to divided attention stimuli (accuracy, response time), car following, and performance during scenarios simulating routine driving as well as crash avoidance situations.

Participants in the simulator study will also be assessed for far visual acuity (Snellen Visual Acuity eye chart; need to have acuity of 20/40 or better, with or without correction), color vision, and contrast sensitivity (Vistech Contrast Sensitivity (Pelli-Robson Chart)). Participants will complete an orientation and practice drive prior to the initial simulation, in order to familiarize them with the controls and roadways.

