4.2.4 Comparison of driving performance between treatment arms

The driving simulation assessments will be conducted in the substudy. (1) Driving measurements (standard deviation of lateral deviation (SDLP) for lane tracking and coherence for car following) following 8 weeks of study medication administration will be compared between treatment arms using ANOVA, to determine whether driving skills will be different after stable cannabis treatment. Acute cannabis effects will be then tested using a covariance pattern model (e.g., unstructured model) including fixed effects of treatment arm, time (minutes), and their interaction. (2) We will also include terms for pain (separately using intensity and relief), its interaction with treatment, and time too, the latter to test for recovery of the cannabis effect back to the Hour 1 baseline level. (3) The correlation (Pearson or Spearman, as appropriate) between blood $\Delta 9$ -THC and each of SDLP and coherence will be estimated at each hour using a 95% confidence interval applied to the Fisher Z-transformation, then back-transformed. Secondary analyses will use independent t-tests or Wilcoxon rank sum tests to compare differences between the means of each of coherence and SDLP for high and low blood $\Delta 9$ -THC levels split at 7 ng/ml. (Aim 3)

4.3 Exploratory analysis:

4.3.1 We will assess the association of daily pain intensity and the dose of treatment (mean daily number of puffs or pills) using a mixed-effects model including fixed effects of dose, treatment regimen, time (i.e., day or week), and dose x treatment regimen interaction, and subject-specific random effect. A significant interaction indicates the association of the dose and pain intensity differs in the three treatment arms. Use of breakthrough pain medication will be then included in the model to remove its confounding effect if it's present. A Non-significant interaction will be removed from the models.

- 4.3.2 Cumulative distributions of maximal pain reduction from baseline among treatment groups will be compared using Kolmogorov-Smirnov tests. This test (nonparametric) will indicate if a given treatment is likely to produce more overall pain reduction than another treatment regimen and takes into account an expected delay in effects of dronabinol compared to whole plant cannabis.

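### The only named test of driving recovery in SAP 4.2.4 conditions on post-dose pain, and its relief version has no Hour 1 value; the planned model without pain should carry the test

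*SAP*

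**What the plan says.** SAP 4.2.4 sets out the driving analysis in numbered steps.

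- Within step (1), after a comparison of arms by ANOVA, acute effects are tested in a covariance pattern model whose fixed effects are arm, time in minutes and the arm-by-time interaction. There are no pain terms.
- Step (2): "We will also include terms for pain (separately using intensity and relief), its interaction with treatment, and time too", followed by "the latter to test for recovery of the cannabis effect back to the Hour 1 baseline level". This is the only place in the SAP where a test of recovery is named.

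The protocol's question is about recovery from the drug as taken. The lay summary (Protocol section 5) says driving simulation is done "to determine how long it takes for them to recover from these medications". Protocol section 9, ARM #2, says the repeat assessments after the first vaporization are there to find when each medication's acute effects have gone. A second dose is given before Hour 6.

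Table 3 in Protocol section 9 gives the schedule. Driving and pain intensity are both marked at Hour 1, before the first dose. The relief row reads "Pain Relief X X X X X X X": seven marks, for Hours 2 to 8, with the Hour 1 cell blank. Section 9 defines relief as a seven-category rating of change made after study medication.

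**The concern.** Two separate things look wrong with step (2) as the home of the recovery test.

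First, pain is downstream of treatment. Aim 1 asks whether active treatment lowers pain relative to placebo, and Protocol section 9, ARM #2, lists spontaneous pain among the acute effects to be measured at the driving visit itself. A model that holds post-dose pain fixed removes any part of the drug's effect on driving that runs through pain. The added pain-by-treatment term also makes the arm difference at any one hour depend on the pain level at which it is read, and the SAP names no level.

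Second, relief has no pre-dose value. A recovery test needs the Hour 1 driving score as its reference. Unless the SAP says how relief is handled at Hour 1, the relief version may be fitted without that reference.

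At stake is whether the answer on recovery describes the drug as participants experience it, or driving at an unspecified fixed level of pain.

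**Working it through.** **Sample size for the substudy (SAP 5.1).** Inputs: 40 per arm, 16% dropout, 87% of completers licensed. 40 × 0.84 = 33.6 (SAP uses 33); 33 × 0.87 = 28.71 (SAP uses 29); 3 × 29 = 87, as stated. The stated 80% power at d = 0.58 can be recovered from a slope formula over visits at weeks 0, 1, 3, 5, 7 and 8 (sum of squares 52) if the within-person correlation is 0.5, which is an assumption because the SAP gives none: (1.96 + 0.842) × √[(2/29) × 64 × 0.5/52] = 0.577. That is the 8-week visit pattern, not the hourly driving schedule, so it does not bear on the recovery test. Only N = 87 is used below.

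**Schedule at the driving visit (Protocol Table 3).** Dosing falls between Hours 1 and 2 and again between Hours 5 and 6.

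| Measure | 1 | 2 | 3 | 4 | 5 | 6 | 7 | 8 |
|---|---|---|---|---|---|---|---|---|
| Driving simulation | X | X | X | | X | X | X | X |
| Pain intensity | X | X | X | X | X | X | X | X |
| Pain relief | | X | X | X | X | X | X | X |

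Recovery from the first dose can therefore be read only at driving Hours 2, 3 and 5, against Hour 1.

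**Rows available to each version, at N = 87 with full attendance.**

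- Step (1), no pain: 7 × 87 = 609.
- Step (2), intensity: 7 × 87 = 609.
- Step (2), relief as a time-varying covariate, rows with a missing covariate deleted: 6 × 87 = 522.
- Lost: 609 − 522 = 87, or 87/609 = 14%. These are all of the Hour 1 rows.

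In that relief model, if time is a factor there is no Hour 1 level and the contrast with Hour 1 cannot be estimated. If time is linear in minutes, the Hour 1 value is an extrapolation, from a line that also crosses the second dose.

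**What adjustment for pain does to the contrast.** Take the active-minus-placebo difference in change from Hour 1 to Hour 5, in SD units of a driving score where higher is worse. Let e be the part not running through pain, g the shift in driving per pain point, and Δ the effect of treatment on pain at Hour 5.

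- Total effect = e + gΔ.
- Effect with pain held fixed = e (linear relation, no unmeasured common cause of pain and driving).
- Adjusted minus total = −gΔ.

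The documents give none of these. Assume e = 0.10 and Δ = −1 point, and vary g. The last two columns come from a simulation with 20,000 per arm, using driving Hours 1, 2, 3 and 5 and leaving out the pain-by-treatment term.

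| g | Total = 0.10 − g | Simulated, no pain term | Simulated, pain in model |
|---|---|---|---|
| −0.1 | 0.20 | 0.21 | 0.11 |
| 0 | 0.10 | 0.09 | 0.09 |
| 0.1 | 0.00 | 0.00 | 0.10 |
| 0.2 | −0.10 | −0.11 | 0.09 |

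The model without pain follows the total effect. The adjusted model stays near 0.10 whatever the total is. It can show residual impairment when the total effect is back to zero (g = 0.1), or understate impairment that remains (g = −0.1). If pain does not affect driving, the two agree.

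**The case against.** The strongest reply is that step (1) already contains the analysis that is wanted. It has no pain terms, uses every driving row including Hour 1, and estimates the total effect over time. Step (2) is introduced as an addition, and the protocol's question about when acute effects cease could be taken to belong to step (1), which the SAP assigns to acute effects. This largely stands. A reader might infer that recovery would be visible only through pain adjustment, or that an unadjusted analysis is missing; the SAP does not support that. What remains is that recovery to Hour 1 is named only in step (2), and no recovery contrast is specified in step (1).

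The wording is also ambiguous: the term meant to test recovery may be time or a pain-by-time interaction. The second would ask whether recovery varies with pain, which is a legitimate explanatory question. Under either reading, though, the named test sits in a model that contains pain.

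On relief, a reader might infer that this version cannot be compared with baseline at all. That goes too far. The loss of Hour 1 assumes that relief enters hour by hour, is left missing at Hour 1, and that such rows are deleted. Hour 1 could be coded as the no-change category, or driving could be analysed as change from Hour 1, as the SAP does for other outcomes. The SAP states none of these, so the fair criticism is an unstated rule. None of them removes the adjustment problem.

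Finally, a reader might infer that a wrong recovery time will feed into safety advice. The documents do not tie this test to any such advice, and the instruction on driving in Protocol section 15 does not depend on it.

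**Conclusion.** The point holds in a limited form. As written, the only named test of recovery to the Hour 1 driving level conditions on post-dose pain, which the trial treats as an outcome of treatment, so it does not estimate the total effect the protocol asks about. This follows from the text and needs no numerical assumption. The direction and size of the discrepancy are unknown; the simulated figures show only that it can go either way, and that it vanishes if pain and driving are unrelated.

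The loss of baseline is conditional and confined to the relief version: 87 of 609 planned driving rows, all at Hour 1, if relief is a time-varying covariate with no Hour 1 rule. The intensity version is not affected by it.

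The endpoint is secondary and lies in the driving substudy. The primary pain comparison is untouched. The change is worth making because the suitable model is already in the plan and moving the test has no real downside.

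**What to change.** Revise SAP 4.2.4 as follows.

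1. Assign the recovery test to the step (1) model of arm, time and arm-by-time, without pain terms. Treat time as a factor, and use arm-by-hour contrasts of Hours 2, 3 and 5 against Hour 1. For each pair of arms this is the change from Hour 1 in one arm minus the same change in the other. State that these hours are used because they precede the second dose.
2. Keep the pain-intensity and pain-relief models, label them explanatory, and state that they are not used for recovery time. Say whether the added term is time or pain-by-time.
3. For the relief version, state the rule for Hour 1: fit it to post-dose hours only, or to driving expressed as change from Hour 1.

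The cost is SAP wording. No new data, visits or participants are needed.

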- Preventing children and adolescents from gaining access to medicinal cannabis because of potential harm to their well-being. Subjects will be required to store cannabis in an area of their home that would prevent anyone else from discovering its location.
- Because some people cannot control their use of cannabis, we will not allow patients with recent substance abuse histories (less than 12 months) to participate.
- We will exclude patients if they are pregnant or refuse to exercise birth control if engaging in sexual activities that could result in pregnancy, have a heart disease or heart rhythm problem or have a history of serious mental illness (e.g., schizophrenia, mania, or a history of hallucinations or delusions)
- In order to avoid carcinogens, we will have subjects use a vaporizer rather than smoke joints or use a water pipe.

- We will instruct subjects not to drive a car or operate heavy machinery for 3-4 hours after use of medicinal cannabis, or longer if larger doses are used or the effects of impairment persist. They will use a designated driver for automobile transportation if they have to go out sooner than 3-4 hours after taking this medicine.
- As the response to cannabis varies widely, participants will titrate to effect and in essence use the minimum amount of medicinal cannabis needed to obtain relief from pain.
- A cannabis withdrawal syndrome will be under surveillance for two weeks; difficulty with getting to sleep and angry outbursts might require that they withdraw from the cannabis more slowly.

The UCSD Department of Psychiatry (Appendix 17) is committed to providing the resources and other supports (e.g., data management and information systems, statistical, and physical performance site) to ensure the timely implementation, conduct, and completion of this program.

Data and Safety Monitoring Board (DSMB)

A DSMB will be selected utilizing a group of experts that will advise the study investigators, with the primary responsibility to monitor human subject safety. The members will be comprised of at least 3 independent clinicians familiar with the conduct of clinical trials. The DSMB will consider study-specific data as well as relevant background information about the test agents and target population under study. The DSMB will review the protocol, including the safety monitoring plan, and identify any major concerns prior to implementation. During the trial the DSMB will review:

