The variables being assessed include vital signs, pain evaluation (cold pressor test), driving simulation, iPad performance testing, blood draws, neuropsychological tests, self-reports (BDI-II, Neuropathic Pain Scale, side effects). The primary outcome will be measured using self-reported average numerical pain intensity during the past 24 hours. A secondary outcome measure will be the level of use of breakthrough pain medication, mood, attention, verbal learning, fine motor coordination, psychomimetic side-effects, and driving performances.

The three main objectives of this study are to 1) assess whether treatment with vaporized whole plant cannabis or oral Δ9-THC reduces spontaneous and evoked pain more than placebo, and whether there are differences between the two active treatments. 2) examine the effects of vaporized whole plant cannabis and oral Δ9-THC (dronabinol) on mood, neuropsychological function, and psychomimetic side-effects (high, stoned, etc.) compared to placebo and to each other. 3) examine the acute effects (after receiving stable treatment for 4 weeks) of vaporized whole

plant cannabis and oral Δ9-THC compared to placebo and each other on driving skills.

2. Baseline characteristics, treatment, and study enrollment summaries

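### The exploratory dose model in SAP 4.3.1 counts dose in puffs or pills, so unless the coding is fixed its vaporized-versus-dronabinol slope contrast and its pooled slope mix units; the breakthrough-medication adjustment also needs an unadjusted result beside it

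*SAP*

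**What the plan says.** SAP 4.3.1, under the exploratory analyses, relates daily pain intensity to "the dose of treatment (mean daily number of puffs or pills". The mixed model is described as "including fixed effects of dose, treatment regimen, time (i.e., day or week), and dose x treatment regimen interaction, and subject-specific random effect". There is one dose term, and no conversion to a common scale is given.

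Two rules follow. On a positive test: "A significant interaction indicates the association of the dose and pain intensity differs in the three treatment arms". On a negative one: "A Non-significant interaction will be removed from the models".

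The same paragraph then says: "Use of breakthrough pain medication will be then included in the model to remove its confounding effect if it's present". It does not say how the presence of confounding will be judged. SAP section 1 gives that variable another role: "A secondary outcome measure will be the level of use of breakthrough pain medication". SAP 4.2 also lists it first among the secondary outcomes.

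The design is double-dummy (Protocol section 9). Each active arm takes the other product's placebo, the third arm takes both placebos, and both products are titrated in everyone. Every participant therefore has a puff count and a pill count. The SAP does not say which count is the dose in which arm, and for double placebo there is no natural choice.

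**The concern.** A regression slope carries the unit of its covariate. If the vaporized arm contributes puffs and the dronabinol arm contributes pills to the same column, the interaction term for those two arms tests whether one puff and one pill go with the same pain difference. That is not the question the SAP says it answers. If the interaction is dropped, the surviving coefficient averages a per-puff and a per-pill slope. Two analysts could also code the double-placebo arm differently and both comply with the text.

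The breakthrough step is a separate matter. Pain prompts breakthrough use, so adjusting pain for it partly conditions on a consequence of the dependent variable. A weaker dose slope after adjustment could then be misread as confounding removed.

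At stake is how a secondary publication on dose and pain would be read. The randomized comparison of pain is not affected.

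**Working it through.** SAP 4.3.1 states no power or error rate, so there is no figure of its own to reproduce.

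**Inputs from the documents**
- Vaporized: 4 to 18 puffs a day (Protocol section 9 and Table 1).
- Oral: 5 mg once daily to 10 mg three times daily, in 5 mg tablets. Table 1 gives 7 to 42 tablets a week, so 7/7 = 1 to 42/7 = 6 a day.
- 33 completers per arm and a 5% level (SAP 5.1).

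**Step 1: unit ratio.** Table 1 maxima for weeks 1, 2, 3 and 4–8, as puffs to tablets per day, are 4:1, 8:2, 12:4 (28/7 = 4) and 18:6. The ratios are 4, 4, 3 and 3.

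**Step 2: slopes.** Suppose a full dose goes with a 1-point fall in pain in both active arms. The slopes are 1/18 = 0.056 per puff and 1/6 = 0.167 per pill, a threefold difference produced by the counting unit. A pooled slope lies somewhere between and describes neither product.

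**Step 3: how often the test would reject.** I simulated the model with a random subject intercept, week as a factor, regimen, dose and dose by regimen, 1,000 runs per setting, with dose following Table 1. These assumptions are not in the documents: each participant takes about 40–100% of the weekly maximum; between-subject SD 1.5 and within-subject SD 1.0; equal dose-response in all three arms when dose is a fraction of its maximum. Ranges cover counting the placebo arm in puffs or in pills.

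| Assumed full-dose effect (points) | Three-arm test, raw counts | Vaporized vs dronabinol slope, raw counts |
|---|---|---|
| 0 | 4–6% | 4–5% |
| 0.5 | 12–13% | 14–15% |
| 1 | 38–46% | 45–47% |
| 1.5 | 71–83% | 78–79% |
| 2 | 92–98% | 95% |

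At 1 point, other SDs (between/within) give 23% (2.0/1.5) and 76% (1.5/0.7) for the three-arm test, with placebo counted in pills. With dose as a fraction of maximum, the three-arm test rejects in about 4–6% of runs throughout.

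**Step 4: the reverse case.** That last result follows from how equality was defined. If the truth is instead an equal slope per puff and per pill (2/18 = 0.11 per unit), raw counts reject in about 5% of runs and the fraction-of-maximum scale in about 94%. The documents favour neither scale.

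**Step 5: breakthrough use.** Assume use = g × pain + noise with SD 1, pain SD 1.8 about the dose line, and a true dose slope of −1.0. After adjustment the slope is −1/(1 + g² × 1.8²):
- g = 0.25: −1/1.2025 = −0.83
- g = 0.5: −1/1.81 = −0.55
- g = 1.0: −1/4.24 = −0.24

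Simulation gave −0.83, −0.54 and −0.22. The values of g and the SDs are assumptions. The calculation also leaves out any effect of breakthrough use on pain, so it shows only one direction of the relation.

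**The case against.** The best reply is that the SAP never says both counts go into one column. Because everyone takes puffs and pills, the model could be fitted once for each, with a common unit and a defined value for double placebo. That would avoid the problem. But the text describes one dose term and one three-arm reading, and says nothing of two fits, so the ambiguity stands. It supports asking for the coding to be stated, not a finding that the analysis is certain to mislead.

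Three stronger readings are tempting and are not supported.
- A reader might infer that a false interaction is likely at some particular rate. The rate runs from about 5% to 98% on assumed effects and SDs, and the artefact needs a non-zero dose-pain slope. If an active arm has a slope and placebo has none, a three-arm interaction is genuine; the unit problem is then confined to the puff-versus-pill contrast.
- A reader might infer that fraction of protocol maximum is the correct scale. Step 4 shows it is another convention: 18 puffs and 6 tablets are titration ceilings, not equivalent exposures.
- A reader might infer that breakthrough use must be left out. The SAP makes the step conditional and places it after the first model. Analgesic use can also confound a day-level association, so dropping it is a trade-off.

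The SAP already calls the result an association. That is right, since Protocol section 15 says "participants will titrate to effect and in essence use the minimum amount of medicinal cannabis needed to obtain relief from pain", so dose responds to pain.

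**Conclusion.** The point holds as a gap in specification. As written, 4.3.1 permits a mixed-unit dose column. Under that coding the stated reading of the interaction does not follow for the vaporized-versus-dronabinol contrast, and the pooled slope has no interpretable unit. These two conclusions need only the threefold to fourfold ratio in Table 1 and, for the contrast, some relation between dose and pain. The rejection rates rest on the assumptions in Step 3 and should be given only as a range. Slopes within a single arm remain valid in their own unit.

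On breakthrough medication, the documents show a variable that is both a listed outcome and a possible confounder; describing the adjustment only as removing confounding is incomplete. Severity is minor: the analysis is exploratory and does not enter the primary comparison, the secondary endpoint analyses or the power calculation.

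**What to change.** Reword SAP 4.3.1 as follows.
1. Enter daily puffs and daily pills as separate terms, or fit two models, each count with its own interaction with regimen, so that active is compared with dummy in the same unit.
2. State that a difference between a per-puff and a per-pill slope will not be read as a difference in dose-response, and that the two will not be pooled, whatever the interaction test shows.
3. If fraction of protocol maximum is shown, label it a sensitivity analysis on an arbitrary scale.
4. Keep the model without breakthrough medication as the main result and report the adjusted model beside it, noting that use may be both a cause and a consequence of reported pain.

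The cost is SAP wording and a recode: the diary already records puffs, oral medication and breakthrough use. The drawback is precision. Both counts are titrated together and will be correlated, so the separate slopes will be less precise. If two models are fitted, the clearest contrasts are vaporized cannabis against double placebo for puffs and dronabinol against double placebo for pills, because in an active arm the dummy count partly tracks the active one.
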